## 1. CLINICAL STUDY SYNOPSIS

| Study Synopsis             |  |
|----------------------------|--|
| Study Title:        | Clinical performance of a new esthetic, self-ligating orthodontic bracket  |
| Sponsor             | 3M Deutschland GmbH
3M Oral Care
[name]
[name], Germany  |
| Investigators       | Principal Investigator:
[name], Dr med dent, PhD
Division of Orthodontics
University of Minnesota
[name]
[name]
[name]
+ 1 [contact]
[contact]

Co-Principal Investigator:
[name], MS
Director, Division of Orthodontics
University of Minnesota
[name]
[name]
[name]
[contact]
[contact] |
| Investigation site  | Division of Orthodontics, University of Minnesota, [name],
[name]  |
| Statistical support | Provided by the Biostatistical Design and Analysis Center (BDAC) at the
University of Minnesota on consultation basis   |

|                                 |   |
|---------------------------------|---|
| Monitor                  | [name]
3M Health Care
Oral Care Solutions
[name]
[name]
[contact]
[contact]   |
| Outcome measure(s)       | Bracket door stability
Ability of door to hold the archwire in the bracket slot
Bracket's ability to rotate teeth
Clinicians' satisfaction with the bracket
Patient comfort in comparison with other brackets   |
| Study Design:            | Prospective, Pilot, Clinical evaluation of a prototype  |
| Estimated # of Subjects: | 30 subjects in 2 cohorts of 15 (no statistical justification, sample size chosen based on number of available brackets)   |
| Patient Population:      | Subjects will be recruited from the pool of individuals undergoing orthodontic treatment at the University of Minnesota.  |
| Test material:           | Lower Anterior EXD-952 Self-ligating Brackets (MBT, 0.022" slot)  |
| Other materials:         | EXD-952 Open/Close Instrument
EXD-952 Debonding Instrument

Clarity Advanced (MBT, 0.022" slot) maxillary brackets
Victory Series low profile (MBT, 0.022" slot) mandibular brackets

0.014" and 0.016" Nickel-Titanium archwires

0.019x0.025" Stainless Steel archwires |

|                               |  |
|-------------------------------|--|
| Subjects:              | 
Inclusion Criteria:
 

• Permanent mandibular dentition including incisors, canines, premolars, and first molars (includes subjects treated with the extraction of premolars)

• Mandibular incisors with sound, non-cariou buccal enamel and no pretreatment with chemical agents such as hydrogen peroxide

 
Exclusion Criteria:
 

• Mental/emotional/developmental disability

• Inability to give informed consent

• Cleft lip and/or palate, craniofacial anomaly, or syndrome

• Obvious oral hygiene issues such as excessive plaque accumulation, gingivitis, and/or pre-existing white spot lesions

• Prosthodontic or restored substrate extending on the labial surface of mandibular incisors

• Deep bite

• Known allergies to any study materials

 |
| Data Analysis Planned: | Calculation of bracket failure rate
Analysis of responses to specifically-designed surveys aimed at determining clinicians' satisfaction with clinical performance of the bracket and patient comfort.  |
| Study Duration:        | Estimated at 2-3 years (until all study subjects have completed orthodontic treatment)   |

|  |  |
|--|--|
| Description of Study Procedure: | 
A cohort of 15 patients starting orthodontic treatment with fixed appliances will receive EXD-952 Ceramic Self-ligating bracket on all mandibular incisors and a different type of brackets on the remaining mandibular teeth. Tooth movement will be initiated using 0.014" or 0.016" Nickel-Titanium archwires.
 
A second cohort of 15 patients will receive EXD-952 Ceramic Self-ligating bracket on all mandibular incisors in a later phase of their ongoing orthodontic treatment. The mandibular incisor brackets will be removed and EXD-952 Ceramic Self-ligating brackets placed instead. Other mandibular brackets will remain in place. Tooth movement will be performed using 0.019x0.025" Stainless Steel archwires.
 
In both cohorts bracket door stability, the ability of the door to hold the archwire in the bracket slot, the bracket's ability to rotate teeth, clinicians' satisfaction with the bracket, and patient comfort in comparison with other brackets will be assessed.
 
The evaluation for each patient will last for at least until one archwire change (cohort 1) or one appointment interval (6-8 weeks, cohort 2).
 
After the evaluation period, EXD-952 Ceramic Self-ligating brackets will remain in place until the orthodontic treatment is completed.
 |
| Reports:                        | 
Reports will be prepared after the initial evaluation period (Initial Report), at the end of each year over the course of the study (Annual Reports), and after all patients have completed treatment (Final Report).
   |

## 2. BACKGROUND INFORMATION

### 2.1 BACKGROUND

Conventional brackets require elastomeric or wire ligatures to hold the archwire in the bracket slot. In contrast, self-ligating brackets use some form of door or clip to secure the wire eliminating the need for elastomeric or wire ligatures. Self-ligating brackets were first conceived in 1935 and there are many designs on the market today. The most popular and well known is the Damon bracket, developed by [name]. Self-ligating brackets have been suggested to offer a number of advantages, including lower levels of friction resulting in more biological forces, decreased treatment times, fewer visits to the office, faster space closure, and fewer periodontal complications.

### 2.2 NAME AND DESCRIPTION OF THE INVESTIGATIONAL PRODUCT

EXD-952 Ceramic Self-ligating Brackets are a new type of esthetic brackets developed by 3M Oral Care Solutions. The brackets have a sliding door and are composed of alumina (aluminum oxide) with small amounts of related oxide compounds (glass powder), which gives them a clear appearance. A nickel-titanium wire serves as part of the door mechanism and is attached to the bracket using 3M ESPE™ Scotchbond™ Universal Adhesive. FDA 510(k) submission of EXD-952 is planned for the end of 2016.

[figure not shown]

Figure 1: EXD-952 bonded to a typodont tooth.

Figure 2: EXD-952 components on a black background show the high translucency of the brackets.

## 2.3 GCP AND REGULATORY REQUIREMENTS

This study will be conducted in compliance with this protocol and GCP including 45 CFR 160 & 164 (Authorization for Use/Disclosure of PHI), 21 CFR 50 (Informed Consent), and 56 (IRBs).

## 2.4 RISK/BENEFIT SUMMARY

The investigational product is expected to qualify as a non-significant risk IDE exempt device. Final risk determination will be made by the Institutional Review Board (IRB) at the University of Minnesota.

### 2.4.1 Risks of Study Participation

The risks associated with the new bracket include wear of enamel surfaces of teeth in contact with the bracket, increased risk of tooth damage when bonded to teeth with large restorations, porcelain crowns, or facings, and losing fractured portions of the bracket in the patient's mouth. However, these risks are not specific to the study and are associated with the use of other ceramic orthodontic brackets as well. Similar to most orthodontic brackets on the market, the new bracket contains nickel and chromium. A small percentage of the population is known to be allergic to nickel and/or chromium.

A risk associated with record keeping is breach of confidentiality. All efforts will be made to keep patient information private. Moreover, patient names will be made anonymous and replaced with a unique identification number. All data will be reported using this number and only the investigators will know which identification number corresponds to which individual.

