#### Cohort 2:

Fifteen patients undergoing comprehensive orthodontic treatment with fixed appliances at the University of Minnesota, who are willing to participate, will have their mandibular incisor brackets removed and EXD-952 brackets placed instead. Other mandibular brackets will remain in place. A rectangular Stainless Steel archwire (0.017x0.025" or 0.019x0.025") will be used as a working mandibular archwire. The perceived ability of the bracket to hold the archwire, ease of handling, and ease of opening/closing the door will be assessed using a custom-designed survey. After the first adjustment visit after placement of EXD-952 brackets (expected 6-8 weeks later) the bracket's ability to control inclination of teeth, clinicians' satisfaction with the bracket, and patient comfort in comparison with other brackets will be assessed using custom-designed surveys. There will be photodocumentation at the bonding appointment and at the adjustment visit. Any bracket failures (e.g. decementation, failure of door etc.) and adverse events will be documented. The initial evaluation for each patient will last for at least one appointment interval (6-8 weeks).

After the evaluation period, EXD-952 Ceramic Self-ligating brackets will remain in place until the orthodontic treatment is completed.

If EXD-952 brackets fail in the course of the study they will be initially replaced with EXD-952 brackets. Should the same EXD-952 brackets fail for a second time in the same patient, all EXD-952 brackets will be removed and replaced with conventional brackets. 3M will cover the cost for replacing failed brackets.

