#### 7.1 ADVERSE EVENTS AND ADVERSE DEVICE EFFECTS

**Adverse Event (AE)** – Any untoward medical occurrence, unintended disease or injury, or untoward clinical signs (including abnormal laboratory findings) in subjects, users or other persons, whether or not related to the tested medical device.

Note 1: this definition includes events related to the investigational medical device or the comparator.

Note 2: this definition includes events related to the procedures involved.

Note 3: for users or other parties, this definition is restricted to events related to investigational medical devices.

**Adverse Device Effect (ADE)** – Adverse event related to the use of a tested medical device.

Note 1: this definition includes adverse events resulting from insufficient or inadequate instructions for use, deployment, implantation, installation, or operation, or any malfunction of the investigational medical device.

Note 2: this definition includes any event resulting from an error use or from intentional misuse of the investigational medical device.

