**Descriptions of reactions or complaints must include:**

- duration
- severity (mild, moderate, severe)
- PI's opinion as to the relationship to the test product (unknown, probably related, or probably not related). If determined "probably not related" was the event: present before the study, due to the primary disease, due to concomitant medications, due to an undercurrent illness, or another reason.
- Photo documentation for internal use will be performed if possible.

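### Section 2.4.1 leaves out the cohort 2 bracket swap as a participation risk, and relatedness is judged only to the product, so harm from removing the old bracket could be under-attributed

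*Combined protocol and SAP*

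**What the plan says.** Section 2.4.1 opens with the device: "The risks associated with the new bracket include wear of enamel surfaces of teeth in contact with the bracket". It goes on to damage to teeth with large restorations, crowns or facings, and to lost bracket fragments. It then adds: "However, these risks are not specific to the study and are associated with the use of other ceramic orthodontic brackets as well". Nickel/chromium allergy and breach of confidentiality complete the list.

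On the cohort 2 procedure, the synopsis states: "The mandibular incisor brackets will be removed and EXD-952 Ceramic Self-ligating brackets placed instead". Section 4.6 (Cohort 2) says that willing patients already in treatment "will have their mandibular incisor brackets removed and EXD-952 brackets placed instead".

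On adverse events, Note 2 to the definition in section 7.1 reads: "this definition includes events related to the procedures involved". The list of what an event description must contain, at the end of section 7.5, asks for the investigator's opinion on the "relationship to the test product (unknown, probably related, or probably not related". If the answer is probably not related, a reason is chosen from a short list that ends in a residual category. Item a) of the sponsor's duties in 7.5 has the sponsor determine relationship to the tested device. The opening of section 7 likewise refers to relationship to the study product.

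**The concern.** Cohort 2 patients have working brackets on their lower incisors. Those brackets are removed, and the teeth bonded again, because the patient joined the study. That additional removal and rebonding is a risk of taking part, separate from the risks of wearing EXD-952. A section on the risks of participation should name it.

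The second half of the concern is classification. If enamel is damaged while the old bracket is coming off, EXD-952 is not yet on the tooth. An investigator asked only about the test product could reasonably answer that the event is probably not related. A safety table built on that answer would then show a study-caused injury among the unrelated events. In a 30-subject feasibility study with purely descriptive statistics (section 8), a few such events could be most of what the safety summary has to say about tooth damage.

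**Working it through.** No figure in the plan is in dispute and the protocol gives no damage rate, so the check is a count and a comparison of sections.

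**Count**
- Cohort 2 has 15 of the 30 subjects (synopsis): "A second cohort of 15 patients will receive EXD-952 Ceramic Self-ligating bracket on all mandibular incisors in a later phase".
- All mandibular incisors means 4 teeth per subject. Section 4.7.1 agrees, since it equates two failed brackets with 50%: 2 / 4 = 50%.
- Teeth with a removal and rebonding: 15 × 4 = 60. Study teeth in total: 30 × 4 = 120. Share: 60 / 120 = 50%. This is before any replacement of failed EXD-952 brackets.

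**Is the swap made only for the study?** Section 4.6 gives no clinical indication. It says the two cohorts allow EXD-952 to be evaluated in different treatment phases and that this information serves business decisions. Study-only is therefore an inference, but no other reason is stated.

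**Is the risk listed elsewhere in 2.4.1?** No. Apart from wear, tooth damage is mentioned there only for teeth with large restorations, crowns or facings. Section 5 excludes mandibular incisors with restored or prosthodontic labial surfaces, so that item applies mainly to teeth the study does not bond.

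**Does the protocol recognise the harm?** Yes. Section 7 names tooth damage at debonding among possible results of the research activity and provides treatment at the sponsor's expense. It does not say which bracket is being debonded.

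**How would an event be classified?**

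| Origin of damage | Adverse event under 7.1? | Relationship item in 7.5 |
|---|---|---|
| Removing the old bracket | Yes (Note 2, procedures) | No procedure category; unknown is possible, and probably not related with the residual reason fits most naturally |
| Bonding EXD-952 | Yes | Concerns the test product; the adverse device effect notes also mention installation and deployment |
| Wearing or debonding EXD-952 | Yes | Concerns the test product |

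The gap is confined to the first row.

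**Could photographs separate the origins?** For cohort 2 the plan is: "There will be photodocumentation at the bonding appointment and at the adjustment visit". No moment is fixed relative to removal. Section 5 requires sound buccal enamel on the incisors, but in cohort 2 the bonded area is under a bracket until the swap. Without an image between removal and rebonding, photographs cannot tell damage from the swap apart from damage at the later EXD-952 debond.

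**The case against.** Several stronger readings are tempting, and the documents do not support them.

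- *The sentence in 2.4.1 is false for cohort 2.* It is not. Its subject is the bracket risks just listed, and it says only that other ceramic brackets share them. It makes no statement about removing existing brackets. The section is incomplete, not wrong.
- *Swap damage would be coded as unrelated.* That cannot be said as a fact. The investigator may also choose unknown or probably related, and harm from bonding EXD-952 concerns the test product. Only harm from taking off the old bracket falls naturally outside.
- *Such harm would go unreported or untreated.* Section 7.4 a) requires every adverse event to be recorded, assessed and reported to the IRB and the sponsor, whatever its relatedness. Sponsor-paid treatment in section 7 is tied to the research activity, not to product relatedness.
- *The IRB is misled.* The determination in section 2.4 concerns the risk status of the product. Under section 10 the IRB also approves the protocol and consent form, and the protocol describes the removal openly in the synopsis and in 4.6. Consent pages are not in the reviewed copy, so disclosure there cannot be judged.

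It is also fair to say that the Adverse Event Report Form itself is not in the documents and that the list in 7.5 is a minimum. The form may already ask about procedures. Nor does the plan exclude a photograph between removal and rebonding.

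What stands is narrower: 2.4.1 omits the step, and every place where the protocol describes a relationship assessment refers to the product or device alone.

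**Conclusion.** The point holds as an omission with a classification gap. Section 2.4.1 does not list the cohort 2 removal and rebonding, which applies to 15 of 30 subjects and 60 of 120 study teeth. The relationship assessment has no study-procedure category although the adverse event definition includes procedures. Damage from removing the old bracket could therefore be classed as probably not related, and study-caused harm under-attributed in the safety summaries. The event itself would still be recorded and reported.

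The conclusion rests on three assumptions: the swap has no clinical reason beyond the study; the event form follows the list in 7.5; and the safety summaries group events by that relationship item. How much harm is involved cannot be estimated, because no damage rate is given. This is a cheap improvement, not an error that invalidates the plan.

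**What to change.** 1. **Section 2.4.1.** Add that in cohort 2 the existing mandibular incisor brackets are removed and the teeth rebonded for the purposes of the study, and list the associated risk of tooth damage. The sponsor should confirm that no other reason for the swap applies. The existing sentence on bracket risks can stay.
2. **Section 7.5, event description list and sponsor review item a), and the event form.** Assess relationship to a study procedure as an item separate from relationship to the test product or device, for both the investigator and the sponsor.
3. **Adverse event summaries (reports under section 4.5).** Tabulate events by both relationship items, by cohort.
4. **Optional, section 4.6, Cohort 2.** At the bonding appointment, where photographs are already planned, add an image of the incisors after removal and before EXD-952 is placed. Keep the image with brackets, so that it can still be compared with the adjustment visit.

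The cost is one extra item on the form, a paragraph of protocol wording and a slightly less favourable risk statement. The optional step adds one image at a visit already scheduled. No extra visits or subjects are needed.

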### 2.4.2 Benefits of Study Participation

Study patients seeking orthodontic treatment will be treated with tooth-colored ceramic brackets without additional charge (\$239 value). They will receive no other direct benefit for participating in this study. However, future orthodontic patients could benefit from the knowledge acquired as the results of this study may help develop better orthodontic materials.

### 2.4.3 Study Compensation

Study patients already undergoing orthodontic treatment will each receive a \$150 gift card upon completion of orthodontic treatment.

## 3. STUDY OBJECTIVES AND PURPOSE

The objective of the study is to evaluate the clinical performance of EXD-952 in orthodontic treatments. Specifically, this study aims at assessing bracket door stability, strength of door to hold the arch wire, the bracket's ability to rotate teeth, clinicians' satisfaction with the bracket, and patient comfort in comparison with other brackets.

## 4. STUDY DESIGN

### 4.1 STUDY TYPE

Prospective, Pilot, Pre-market feasibility study/Clinical evaluation of a prototype.

#### 4.2 STUDY MATERIALS

EXD-952 Ceramic Self-ligating Brackets  
Open/Close Instrument for EXD-952 Self-Ligating Ceramic Brackets  
Debonding Instrument for EXD-952 Self-Ligating Ceramic Brackets

#### 4.3 OTHER MATERIALS

Victory Series Low Profile brackets for remaining mandibular teeth  
Clarity Advanced brackets for maxillary teeth  
Transbond XT light-cure adhesive and primer

#### 4.4 ESTIMATED STUDY TIMELINE

|                            |            |
|----------------------------|------------|
| Start of Study:            | 2016-12-01 |
| End of Initial Evaluation: | 2017-03-01 |
| End of Study:              | 2020-03-01 |

The estimated study timeline above is based on previous experiences with clinical studies carried out at the Division of Orthodontics at the University of Minnesota. The actual timeline will depend on factors such as IRB review time, subject recruitment, and duration of orthodontic treatment of the study participants.

#### 4.5 REPORTING PERIODS

The PI will provide the Sponsor with the following written reports:

Initial report: This report will be provided within 60 days after all study subjects in cohort 1 have completed one archwire change and all subjects in cohort 2 had at least one adjustment visit after placement of the investigational brackets. This report will include data related to the primary outcome measures.

Annual progress reports: Progress reports will be provided annually and will include data on bracket failure and adverse events until all study subjects have completed orthodontic treatment.

Final report: A final report will be provided after all study subjects have completed orthodontic treatment.

#### 4.6 STUDY PROCEDURES

The study will involve two patient cohorts – (1) a cohort of patients seeking orthodontic treatment and (2) a cohort of patients already receiving orthodontic treatment with fixed appliances.

This way, the robustness and performance of EXD-952 can be evaluated in different treatment phases. The information acquired in the different treatment phases is important for business decisions.

#### Cohort 1:

Fifteen consecutive patients presenting for comprehensive orthodontic treatment with fixed appliances at the University of Minnesota, who are willing to participate, will have their maxillary incisors, canines, and premolars bonded with conventional ceramic orthodontic brackets (Clarity Advanced, 3M), mandibular incisors bonded with self-ligating ceramic orthodontic brackets (EXD-952, 3M), and mandibular canines and premolars bonded with conventional metal brackets (Victory Series Low Profile, 3M). A Nickel-Titanium archwire (0.014" or 0.016") will be used as an initial mandibular archwire. The perceived ability of the bracket to hold the archwire, ease of handling, and ease of opening/closing the door will be assessed using a custom-designed survey. After the first archwire change (expected 6-8 weeks after initial bonding) the bracket's ability to rotate teeth, clinicians' satisfaction with the bracket, and patient comfort in comparison with other brackets will be assessed using custom-designed surveys. There will be photodocumentation at the initial appointment and at the first archwire change to assess the bracket's ability to rotate teeth. Any bracket failures (e.g. decementation, failure of door etc.) and adverse events will be documented. The initial evaluation for each patient will last for at least until one archwire change.

After the evaluation period, EXD-952 Ceramic Self-ligating brackets will remain in place until the orthodontic treatment is completed.

